11 CRITERIA FOR EVALUATION AND ENDPOINT

11.1 Feasibility

To evaluate the feasibility to conduct a trial of AT for CIPN + standard of care therapy. Primary feasibility objectives will be evaluated in terms of recruitment (enrollment of 20, average of 2 eligible women per month to participate in the trial, identification of appropriate recruitment strategies, the appropriateness of eligibility criteria), retention (70% or more participants comply with AT attendance defined as 8 or more of 10 AT sessions, and complete both fMRI scans), safety (zero serious adverse events directly related to AT) and questionnaire completion (70% or more enrolled participants comply with data collection).

Primary outcome measures: Mean enrollment, completion rate of AT and fMRI, rate of serious adverse events, rate of questionnaire completion.

11.2 Safety

The DSMC will consist of the appropriate Huntsman Cancer Institute (HCI) DSMC members.

Overall safety of this study will be assessed using the CTCAE (NCI Common Terminology Criteria for Adverse Events) version 5.0 and the following safety and tolerability endpoints will be used:

-incidence of treatment-emergent adverse events associated (TEAE's) with acupuncture- known TEAE's detailed below.

Patients will be instructed to disclose all study-related side-effects, symptoms or AEs. Potential adverse effects of acupuncture treatment include: Bruising Bleeding Needle shock Pre-syncope (Dizziness) Diaphoresis (Sweating) Nausea and Vomiting Loss of consciousness

The main side effects of acupuncture include a slightly increased risk of minor bruising and bleeding and rarely infection. Needle shock, a vaso-vagal response to needle insertion, occurs about 5% of the time usually during the first or second treatment. Patients may become faint, diaphoretic, nauseated and occasionally lose consciousness. These are often reversible by removing the acupuncture needles and laying the patient supine.

-incidence of procedure-related adverse events associated with fMRI (source: FDA)

MR images are made without using any ionizing radiation, so patients are not exposed to the harmful effects of ionizing radiation. But while there are no known health hazards from temporary exposure to the MR environment, the MR environment involves a strong, static magnetic field, a magnetic field that changes with time (pulsed gradient field), and radiofrequency energy, each of which carry specific safety concerns:

• The strong, static magnetic field will attract magnetic objects (from small items such as keys and cell phones, to large, heavy items such as oxygen tanks and floor buffers) and may cause damage to the scanner or injury to the patient or medical professionals if those objects

become projectiles. Careful screening of people and objects entering the MR environment is critical to ensure nothing enters the magnet area that may become a projectile.

- The magnetic fields that change with time create loud knocking noises which may harm hearing if adequate ear protection is not used. They may also cause peripheral muscle or nerve stimulation that may feel like a twitching sensation.
- The radiofrequency energy used during the MRI scan could lead to heating of the body. The potential for heating is greater during long MRI examinations.

Acupuncture Schedule Adjustments

The main toxic effects of acupuncture include a slightly increased risk of minor bruising and bleeding and rarely infection. Needle shock, a vaso-vagal response to needle insertion, occurs about 5% of the time usually during the first or second treatment. Patients may become pre-syncopal, diaphoretic, nauseated and occasionally lose consciousness. These symptoms are easily reversible by removing the acupuncture needles and laying the patient supine. There are no universal guidelines in patients with lymphoedema however there may be hospital, academic medical center, or department specific guidelines. These concerns can adequately be addressed by the Study Acupuncturist as toxic effects of acupuncture are taught in all acupuncture schools.

Reporting adverse events and referrals for patient care

During the study, all study patients will be under the care of either a medical oncologist or a surgical oncologist. If any abnormalities or problems, including possible study related adverse events (AE) or reportable serious adverse events(SAEs), are detected during screening, subsequent measurements, or study activities, the patient will be referred back to their medical provider for appropriate care. The SC and study primary investigators (PIs) will be responsible for recording and reporting any intervention related AEs and reportable SAEs. The possible routes of referral are as follows:

a. Abnormality/problem detected during screening and subsequent clinic visits: The SC will notify and discuss with the study PIs. The responsible site investigator as appropriate will refer the patient to their medical provider. The SC and study PIs will record and report any study-related AEs and reportable SAEs as appropriate.

b. Abnormality/problem detected during telephone contact: The SC will refer the patient to their medical provider and the responsible site investigator as appropriate. The SC and study PIs will record and report AEs and reportable SAEs as appropriate.

c. Abnormality/problem detected during acupuncture session: The Study Acupuncturist will notify and discuss with the responsible site investigator. The SC will be notified and the SC and the responsible site investigator as appropriate will refer the patient to their medical provider. The SC and study investigators will record and report as appropriate.

More on adverse event procedures are outlined in section 16.4.1

11.3 Stopping Rules

Conditions that may lead to reasonable cause and warrant termination of this study include, but are not limited to:

- -Subject or investigator noncompliance
- -Unsatisfactory subject enrollment
- -Lack of adherence to protocol procedures
- -Lack of valuable and/or complete data
- -Potentially unacceptable risk to study subjects

12 STATISTICAL CONSIDERATIONS

Data will be collected via REDCap and analyzed with SPSS. Missing data will be handled with imputation of the median value of all available data for each individual item.¹⁹

Demographics: Analysis of demographic data will consist of calculating means, standard deviations, frequencies, and proportions. Demographic information to include: age, marital status, race and ethnicity, current medications and medical history.

Feasibility data: will be analyzed by calculating frequency and percentages, specifically:

- **Recruitment** frequency count (enrollment of 20 women, average of 2 eligible women per month to participate in the trial, identification of appropriate recruitment strategies, the appropriateness of eligibility criteria),
- **Retention** frequency and percentage (70% or more participants comply with 8 or more AT sessions and complete both fMRI scans)
- Safety frequency count (zero serious adverse events directly related to AT)
- **Questionnaire completion** frequency and percentage (70% or more enrolled participants complete at least 80% of questions at all protocol-directed time points).

Questionnaires: analyses will consist of student t-test and chi square computations according to the type of data.

- CIPN-20
- CIPN-R-ODS
- BPI
- Multidimensional Assessment of Interoceptive Awareness (MAIA-2)

Functional MRI quantification: Volume and Surface preprocessing pipelines from the Human Connectome Project will be executed for each resting sequence on completion of structural preprocessing. MultiEcho ICA Cleaning: All resting state data will additionally be processed using MultiEcho ICA pipeline (AFNI) allowing removal of non-neural components in the BOLD data. Head motion: Rigorous control of head motion begins before acquisition with subject training and instruction, continues during scanning with repeated reminders to hold still and analysis of image quality after each scan with repetition as possible, and postprocessing including voxelwise despiking, motion parameter estimation and correction, physiologic waveform regression, Multiecho ICA cleaning, and volume censoring (scrubbing). Post-hoc mean and maximal root-mean-square head motion estimates will be used as covariates for all biomarkers. Connectivity: Time series will be estimated FreeSurfer-defined subject-specific regions of interest in somatosensory cortex, anterior cingulate, anterior insula, amygdala, thalamus, medial prefrontal cortex, orbitofrontal cortex, and precuneus, as well as at 361 ROIs for graph-theoretic and network analyses (modularity and clustering coefficient) comprising 333 cortical ROIs strategically positioned at network hubs, 14 cerebellar ROIs, and 14 subcortical gray matter ROIs defined from Freesurfer segmented subject specific nuclei.

Functional MRI Analysis: We will analyze functional connectivity using a parcellation covering the cortical and subcortical gray matter at 5 mm resolution. Brain parcellation will be constructed by assessing regions of interest (ROIs) and measuring each voxel, which can represent a million brain cells. Each voxel will be tested in sequence beginning with the inferior left voxel in the cerebellum. If a voxel is greater than 5 mm distant to voxels already selected, then this voxel will be included in the set of ROI center coordinates.

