	feasibility data will consist of calculating
	frequencies and percentages Analysis of
	questionnaires will consist of within-

group pre/post analysis with student t-test and chi square with significance will be set at .05 and two-tailed hypotheses.
Sample Size Estimation: A sample size of 25-30 participants is ideal for a pilot feasibility study ¹ . However, we are recruiting only 20 participants due to funding constraints.

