1.2 Secondary Objectives and Endpoints

To evaluate the impact of AT on the reported experience of CIPN.

- 1.2.1 To evaluate central pain processing and cortical connectivity in patients with CIPN treated by acupuncture by analyzing fMRI of all participants.
- 1.2.2 To evaluate if there is any change in patient-reported measures from before AT to after study completion.

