5.1 Inclusion Criteria Yes/No (Response of "no" = patient ineligible)

- 5.1.1 _____ Female age 18 or older.
- 5.1.2 Histologically proven breast, uterine, cervical or ovarian cancer of any stage.
- 5.1.3 Received either (1) a Paclitaxel treatment dose of at least 480 mg/m² paclitaxel as a single or combination agent or (2) a Docetaxel treatment dose of at least 150 mg/m² docetaxel as a single or combination agent. Treatment must be completed at least 3 months prior to enrollment.
- 5.1.4 Eligible patients report at least 1 month of altered sensation and/or pain in the feet (with or without presence in one or both hands) with a score of greater than or equal to 20 for CIPN on the sensory subscale of the CIPN-20 (scale 0-100).

5.1.5. _____ Able to provide informed consent and willing to sign an approved consent form that conforms to federal and institutional guidelines.

5.1.6. ECOG status of 0 (asymptomatic), 1 (symptomatic but completely ambulatory) or 2 (symptomatic, <50% in bed during the day).

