10 STUDY PROCEDURES

This study will enroll female patients who have completed treatment with either paclitaxel or docetaxel at least three months prior. Paclitaxel is a neurotoxic chemotherapy known to cause CIPN. Docetaxel is also a neurotoxic chemotherapy known to cause CIPN. Patients must have experienced at least one month of altered sensation in feet (with or without

presence in one or both hands) and/or pain with a score of greater than or equal to 20 for CIPN on the sensory subscale of the CIPN-20. We will commence recruitment 3 months after patients have completed their last chemotherapy dose.

Patients will be recruited from the Huntsman Cancer Center Oncology Clinics in collaboration with their oncologists.

For this study, enrollment will be limited to patients with breast, ovarian, cervical, endometrial, or uterine cancer with CIPN and completed chemotherapy treatments.

Visits:

Screening Visit:

Potentially eligible subjects will be scheduled for a screening visit. After informed consent is obtained, the SC will review and confirm inclusion/exclusion criteria. The SC will take a brief medical, history and administer the CIPN-20 questionnaire. If all inclusion and exclusion criteria are fulfilled, the subject will be scheduled for a baseline visit. This visit may occur on the same day as screening, but must occur within 2 weeks of study screening visit. If the participant has received treatment outside of University of Utah Health a medical record release form will be initiated and submitted as appropriate.

Baseline Visit:

Patients diagnosed with breast, ovarian, cervical, endometrial, or uterine cancer who will be treated with paclitaxel or docetaxel chemotherapy associated with CIPN will undergo a number of questionnaires. The patient will then be enrolled in the study and scheduled in the Wellness Center for acupuncture therapy (AT). All participants will be scheduled for fMRI, which must occur within nine days after baseline.

Participants will undergo study interview and fMRI within 9 days after baseline following enrollment.

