Appendix C: Brief Pain Inventory (BPI)

4 Items are scored from 0 'no pain' to 10 'pain as bad as you can imagine'

1 item is scored 0% 'no relief' to 100% 'complete relief' regarding how much relieve pain treatments or meications provided.

7 items ar rated from 0 'does not interfere' to 10 'completely interferes' regarding pain interference.

1903 ASE USE CK INK PEN	Da Su Str	te: (month) bject's Initial udy Subject	/ (day) / [) (y	rear)	Study Na Protocol PI: Revision:	#: 07/01/05			
7. What	treatn	nents or ma	edications	are you		g for your	pain?			
8. In the mark t 0% 1 No Relief	last 2 he bo 0%	4 hours, ho x below the 20%	ow much i e percenta 30%	relief hav age that r 40%	ve pain tre most sho 50%	eatments ws how m 60%	or medica nuch relia 70%	ations pro of you hav 80%	90%	lease ed. 100% Complete Relief
9. Mark f with ye A. Gen 0 Does Not Interfere	the bo our: eral /	x beside th Activity 2	e number (that desc	ribes how	, during th	e past 24	hours, pai	in has inte	10 Completel Interferes
B. Moo 0 Does Not Interfere	od 1	2	□3	4	5	6	7	8	9	Completel
C. Wall 0 Does Not Interfere	king (□3	4	5	6	7	8	9	Complete Interferes
D. Nor 0 Does Not Interfere	mai v	vork (incl 2	udes bo				me and 7	nousew 8	ork) 9	Complete Interferes
Does Not Interfere		2		4	5	6	7	8 []	9	Complete Interferes
0 Does Not Interfere	1 oyme	2 nt of life	3	4	5	6	7	8 []	9	Complete Interferes
0 Does Not Interfere	1	2	3	4	5	6	7 []	8 🗌	9	Completel Interferes
Page 2 of 2	2		с	opyright 199 Pair Al	1 Charles S. n Research G I rights reserv	Cleeland, Phi roup red	D			

Appendix D: Multidimensional Assessment of Interoceptive Awareness (MAIA-2) 37 items are rated from 0 'never to 5 'always'

Below you will find a list of statements. Please indicate how often each statement applies to you generally in daily life.

	C	ircle o	each line			
	Neve	r				Always
1. When I am tense I notice where the tension is located in my body.	0	1	2	3	4	5
2. I notice when I am uncomfortable in my body.	0	1	2	3	4	5
3. I notice where in my body I am comfortable.	0	1	2	3	4	5
4. I notice changes in my breathing, such as whether it slows down or speeds up.	0	1	2	3	4	5
5. Lignore physical tension or discomfort until they become more severe.	0	1	2	3	4	5
6. I distract myself from sensations of discomfort.	0	1	2	3	4	5
7. When I feel pain or discomfort, I try to power through it.	0	1	2	3	4	5
8. I try to ignore pain	0	1	2	3	4	5
9. I push feelings of discomfort away by focusing on something	0	1	2	3	4	5

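### Filling blank questionnaire items with the group median understates the error of the secondary pre/post change (per-visit median) or shrinks a real change (pooled median)

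*Combined protocol and SAP*

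**What the plan says.** Section 1.2.2 sets a secondary objective: "To evaluate if there is any change in patient-reported measures from before AT to after study completion". The Study Summary makes the comparison within-group: "group pre/post analysis with student t-test and chi square with significance will be set at .05 and two-tailed hypotheses". Section 12 repeats the method ("analyses will consist of student t-test and chi square computations according to the type of data") and opens with the missing-data rule: "Missing data will be handled with imputation of the median value of all available data for each individual item".

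The documents do not say whether the median is per visit or pooled over visits, how many filled items a score may contain, or whether a wholly missed form is filled. They give no variance correction, no sensitivity analysis and no expected missing rate.

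Two related passages matter. The completion criterion in Section 12 asks that women "complete at least 80% of questions at all protocol-directed time points", without saying whether this is counted before or after filling, or how not-applicable questions count. Appendix A lists CIPN-20 item 19 for drivers only and item 20 for males only, while inclusion criterion 5.1.1 admits women only.

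**The concern.** A group median ignores the woman's own other answers, although items of one subscale are correlated and her answers are the best guide to the blank. The t-test then treats the filled value as data.

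- **Per-visit median.** Filled items carry no between-woman variation, so the spread of the change scores falls while the true sampling error does not. The reported standard error (SE) is too small.
- **Pooled median.** A blank receives the same value before and after treatment. An item blank at both visits contributes zero change, and the mean change is pulled toward zero.

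At stake is the trustworthiness of the secondary patient-reported results. There is also a gap that needs no assumption: item 20 has no available data in an all-female trial, so the rule yields no value for one of the three autonomic items. On item 19, one of eight motor items, non-drivers would be given the drivers' median. Neither item belongs to the sensory scale.

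**Working it through.** The plan states no standard deviation, effect size, correlation or missing rate, so there is no figure of its own to reproduce.

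**Inputs from the documents.** n = 20 (Section 4.3); two-sided .05 within-group test (Study Summary); nine sensory items scored 1 to 4 (Appendix A); entry only with a sensory score of at least 20 on 0-100 (criterion 5.1.4). At screening the coordinator takes a "brief medical, history and administer the CIPN-20 questionnaire", so blanks after treatment are likelier than blanks at entry. Both patterns are shown.

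**Assumptions.** 5, 10 or 20% of items blank completely at random. The 20% is an upper-end case: it is the shortfall at which one woman still counts as complete, applied to everyone. Latent-trait items with loading 0.7, trait correlation 0.6 across visits, item-error correlation 0.4 and answer shares 46/31/16/7%; no treatment effect; 20,000 runs per cell. The entry cut alone makes the mean fall by about 6.7 points, so error is measured against the complete-data mean change, not against zero.

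**1. Per-visit median, CIPN-20 sensory scale**

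| Blank | Miss rate, both visits | Miss rate, post only | SE too small by (both / post) |
|---|---|---|---|
| 5% | 6.1% | 6.1% | 6% / 5% |
| 10% | 7.9% | 7.2% | 12% / 9% |
| 20% | 12.0% | 9.7% | 24% / 16% |

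Check by hand at 20% blank, using reported SE over actual standard deviation of the estimate:
- Both visits: 4.03 / 5.28 = 0.763. The critical value 2.093 (19 df) then acts as 2.093 × 0.763 = 1.60, with two-sided tail 12.7%.
- Post only: 4.26 / 5.10 = 0.835; 2.093 × 0.835 = 1.75; tail 9.7%.

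The same step at 5% blank, with ratios 0.94 and 0.95, gives 6.4% and 6.1%. Loadings of 0.5 and 0.85 at 20% blank give 12.7 and 12.6% (both visits), 10.5 and 9.5% (post only). Post-only blanks also shift the mean toward improvement by 0.2 / 0.4 / 0.7 point, because the median of a skewed item lies below its mean.

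**2. Pooled median, CIPN-20 sensory scale**
- Both visits, 20% blank: the change goes from -6.66 to -5.30, and 5.30 / 6.66 = 0.80, a shrinkage of 20%. At 5 and 10% blank it is 5 and 10%.
- Post only, with an assumed 0.5 SD latent treatment effect: -17.2 becomes -15.8 at 20% blank (1.4 / 17.2 = 8%), and -17.1 becomes -16.7 at 5% (0.4 / 17.1 = 2%).
- In the runs without a treatment effect, the miss rate stays at 4.9 to 5.8%.

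**3. Other scales, per-visit median, at 5 / 10 / 20% blank**
- BPI interference (seven 0-10 items, no entry cut on this scale): 6.2 / 8.6 / 13.1% (both visits); 5.7 / 6.4 / 8.3% (post only).
- 37 symmetric 0-5 items resembling MAIA-2: 6.2 / 7.3 / 11.3%; 5.2 / 6.0 / 7.1%.

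**4. Scoring from answered items, same cells:** miss rate 4.6 to 5.3%, bias at most 0.02 point.

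**5. Not-applicable items and the 80% criterion.** The four forms hold about 20 + 28 + 12 + 37 = 97 questions. Items 19 and 20 are 1 to 2 of 97 (1 to 2%), or 1 to 2 of 20 (5 to 10%) if the criterion is applied to the CIPN-20 alone.

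**The case against.** **Size.** The documents give no missing rate, 20% blank for every woman is extreme, and at 5% blank the per-visit miss rate is 5.2 to 6.2% across the scales simulated. Pooling fits the wording at least as well as a per-visit median, and then the miss rate is near nominal when there is no treatment effect. This stands. It limits the point without removing it, because pooling trades the error-rate fault for shrinkage.

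**The .05 level.** A reader might infer that the fill is what breaks the .05 level on the CIPN-20. It is not. Women are selected on a high sensory score, so scores fall on average without any treatment effect, and complete data already reject zero in about 26% of such simulated trials. Answered-item scoring leaves that at 24 to 26% at 20% blank.

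**The later trial.** A reader might also infer that a shrunken effect will mis-size the planned randomised trial. Section 2 says that the pilot lays a foundation and shows that team and location are in place. No passage says that the pre/post change will be carried forward.

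**Intervals.** The plan mentions tests, not confidence intervals. The interval used here is the one that goes with the planned paired t-test.

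**The remedy.** Answered-item scoring looks safe above partly because the simulated items are alike and the blanks random. With unequal items and post-only blanks confined to two rarely endorsed ones, it was off by 3.7 points with a 10.4% miss rate, against about 5% for median filling. This stands, and the fix needs a guard.

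**Items 19 and 20.** They affect neither eligibility nor the sensory scale. True, but the rule as written still gives no answer for one and a poor answer for the other.

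**Conclusion.** The point holds as a minor to moderate one, confined to the secondary patient-reported results. Under a per-visit median the SE is understated: on the CIPN-20 sensory scale the interval misses about 6 to 7% of the time at 5% blank and 10 to 12% at 20%. Under a pooled median a real change shrinks, by about the blank fraction with blanks at both visits and by about 8% at 20% blank with post-only blanks. At 5% blank or less the effect is small. These sizes rest on an assumed blank rate, random blanks and assumed item correlations.

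The primary feasibility counts are unaffected provided completion is counted on raw answers, which the plan should state. That the rule cannot be applied to item 20 rests on no assumption.

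**What to change.** Replace the median sentence in Section 12 with these rules:

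1. Score each subscale from the woman's own answered, applicable items when at least half are answered. The half is a suggested threshold, not one from the documents.
2. Because items differ in how often they are endorsed (the CIPN-R-ODS runs from leaving bed to running), also compute the change from items answered at both visits as a check. If blanks cluster on particular items, use a method that allows for item difficulty, or multiple imputation conditioning on the woman's other answers and baseline.
3. Do not impute not-applicable items or wholly missed forms; test observed pairs.
4. Count the 80% completion criterion on raw answers, with not-applicable items out of the denominator.
5. Report missing items and missing forms per visit.

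The cost is a few sentences and no new data. Intervals are slightly wider than with complete data: at 20% blank the mean SE is 5.10 against 4.78 with blanks at both visits (5.10 / 4.78 = 1.07), or 4.92 against 4.77 post only (1.03). Bias remains possible if blanks are not random, for example if sicker women miss whole forms. Rules 2 and 5 help to show clustered or uneven blanks but do not remove that risk.

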1 OBJECTIVES

This pilot study aims to evaluate the feasibility to conduct a study of acupuncture treatment (AT) for Chemotherapy-Induced Peripheral Neuropathy (CIPN) at Huntsman Cancer Institute and to investigate changes in physiological biomarkers when using acupuncture to treat CIPN.

1.1 **Primary Objectives and Endpoints**

To evaluate the feasibility to conduct a trial of AT for CIPN + standard of care therapy. Primary feasibility objectives will be evaluated in terms of recruitment (enrollment of 20 women, average of 2 eligible women per month to participate in the trial, identification of appropriate recruitment strategies, the appropriateness of eligibility criteria), retention (70% or more participants comply with 8 or more AT sessions and complete both fMRI scans), safety (zero serious adverse events directly related to AT) and questionnaire completion (70% or more enrolled participants comply with all data collection).

1.1.1 Primary outcome measures: Mean enrollment, completion rate of AT, fMRI, rate of serious adverse events, rate of questionnaire completion.

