4.3 Number of Patients

Twenty participants will be enrolled. Sample size for this pilot feasibility study is determined by budgetary constraints. While a sample of 25-30 would be ideal for the aims of this study¹, we are limited by our study budget to twenty participants.

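### The primary feasibility proportions are reported without any interval, so a met criterion at n=20 carries no measure of precision

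*Combined protocol and SAP*

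**What the plan says.** Section 1.1 makes recruitment, retention, safety and questionnaire completion the primary objectives: "Primary feasibility objectives will be evaluated in terms of recruitment", followed by the other three domains. Section 12 gives the analysis. Feasibility data "will be analyzed by calculating frequency and percentages", with these criteria:

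- Retention: "70% or more participants comply with 8 or more AT sessions and complete both fMRI scans". Section 11.1 words it as "70% or more participants comply with AT attendance defined as 8 or more of 10 AT sessions, and complete both fMRI scans". Both treat it as one composite of sessions and scans.
- Questionnaires: "70% or more enrolled participants complete at least 80% of questions at all protocol-directed time points".
- Safety: a count, with the target "zero serious adverse events directly related to AT" (Section 1.1, repeated in Sections 11.1 and 12).

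The Study Summary and Section 10 also describe these criteria only as counts, rates and percentages. On sample size, Section 4.3 says "Twenty participants will be enrolled. Sample size for this pilot feasibility study is determined by budgetary constraints", and adds: "While a sample of 25-30 would be ideal for the aims of this study". It does not say what precision either size gives. The only significance level in the document, 0.05 two-tailed, is set in the Study Summary for the pre/post questionnaire comparisons.

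**The concern.** A percentage from 20 women compared with a fixed cut-off yields a yes or no, with nothing to show how firmly the answer is supported. These are the study's primary endpoints, and Section 2 presents the pilot as preparation for a later randomised trial. If the report says only that the criterion was met at 70%, a reader cannot see that the true rate could plausibly be below one half. If it says only that no related SAE occurred, a reader cannot see how large a rate remains compatible with that result. The secondary questionnaire outcomes get significance tests, while the primary endpoints get no statement of uncertainty.

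**Working it through.** **Inputs from the document.** n = 20 (Section 4.3); cut-offs of 70%, 70% and zero (Section 12). The sample size has no statistical derivation, so there is no planned figure to reproduce.

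**Assumptions.** Exact (Clopper-Pearson) intervals at a two-sided 95% level; all 20 enrolled women in each denominator; each woman counted once for related SAEs; independent outcomes.

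**Step 1, threshold count.** 0.70 × 20 = 14, so each 70% criterion is met at 14/20 or better.

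**Step 2, interval at the threshold.** The lower limit is the 0.025 quantile of Beta(14, 7) = 45.7%. The upper limit is the 0.975 quantile of Beta(15, 6) = 88.1%. Other methods give similar limits for 14/20: Wilson 48.1% to 85.5%, Agresti-Coull 47.9% to 85.7%, Jeffreys 48.3% to 86.4%, Wald 49.9% to 90.1%. The choice moves a limit by about four points at most.

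**Step 3, result needed to exclude 70%.** The exact two-sided lower limit is 68.3% at 18/20 and 75.1% at 19/20, so it first exceeds 70% at 19/20.

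**Step 4, behaviour of the rule.** The chance of passing is P(X ≥ 14) with X ~ Binomial(20, p):

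| True rate | Chance of passing |
|---|---|
| 46% | 2.7% |
| 50% | 5.8% |
| 55% | 13.0% |
| 60% | 25.0% |
| 65% | 41.7% |
| 70% | 60.8% |
| 75% | 78.6% |
| 80% | 91.3% |
| 88% | 99.3% |

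**Step 5, zero related SAEs.** The upper limit solves (1 − p)^20 = 0.025, so p = 1 − 0.025^(1/20) = 16.8%. A one-sided 95% bound would be 1 − 0.05^(1/20) = 13.9%. The chance of seeing none in 20 is 0.99^20 = 81.8% at a true rate of 1%, 0.95^20 = 35.8% at 5%, and 0.90^20 = 12.2% at 10%.

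**Step 6, the size called ideal.** The smallest passing results are 18/25 (50.6% to 87.9%) and 21/30 (50.6% to 85.3%). The larger sample narrows the interval only modestly.

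**Step 7, denominator.** The questionnaire criterion refers to enrolled women. The retention criterion refers only to participants, and Section 7.4 removes women with fewer than 8 sessions from the study. As an illustration with assumed counts: if 12 of 20 met the composite and 5 were removed for too few sessions, retention is 12/20 = 60% (not met) or 12/15 = 80% (met). An interval means little until this is settled.

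**The case against.** The strongest reply is that a small single-arm pilot may properly be descriptive. The document admits its sample is below what it considers ideal, and anyone given the counts can compute an interval later. Safety does not rest on the zero count alone either: Section 11.2 adds the incidence of treatment-emergent and fMRI-related adverse events, and Section 16.3 provides for committee review of reportable SAEs. All of this stands, and it keeps the point modest. It does not remove it, because an interval is itself descriptive, and naming the method and denominator beforehand prevents a choice made after the results are known.

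A reader might infer three stronger things that the documents do not support.

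- *That the 70% rule cannot tell a poor rate from a good one.* The width of the interval at exactly 14/20 describes the barest pass. The rule itself separates a true 46% from a true 88% very well (2.7% against 99.3%).
- *That the missing interval makes the decision close to a coin toss.* Any cut-off placed at the true rate behaves that way. With a true rate of 70%, the chance of passing is 61% at n = 20, 59% at n = 30 and 55% at n = 100. An interval neither causes nor cures this.
- *That the investigators will declare acupuncture safe on zero events, or will use these percentages to design the next trial.* The document says neither. Section 2 states the specific aim as showing that the team and site are in place.

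**Conclusion.** The point holds as a gap in precision and reporting, not as an arithmetic error or a faulty decision rule. The primary retention, questionnaire and related-SAE criteria are to be reported with no measure of uncertainty. At 20 women that uncertainty is large: 46% to 88% around a minimum pass, and up to 16.8% after zero related SAEs. The rule is weak where the true rate lies between about 55% and 75%, the region around its own cut-off.

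The figures rest on the exact method, a two-sided 95% level and a denominator of all 20 enrolled. The document fixes none of these except the enrolled denominator for questionnaires. Another interval method would not change the conclusion; a different retention denominator could change the percentage itself. The point covers these three criteria only, not mean monthly enrolment, which is also a primary measure.

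**What to change.** In Section 12, keep the 70% and zero cut-offs as the progression criteria and add the following:

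- Report the composite retention rate (8 or more sessions and both scans), the questionnaire-completion rate and the proportion of women with a related SAE, each with an exact (Clopper-Pearson) two-sided 95% confidence interval.
- Use all enrolled women as the denominator for each, including those removed for fewer than 8 sessions.
- State each conclusion as criterion met or not met, together with its interval. Do not present it as proof that the true rate is at least 70% or that acupuncture carries no serious risk.

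No extra participants or hypothesis tests are needed. The cost is a few lines of analysis and a conclusion that will look less favourable.
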